## 5.3 Subgroup analysis

As per the subgroup analysis stated in the Statistical Analysis Plan, subgroup analysis will be conducted on initial fracture management (surgical vs non-surgical).

# 6 Reporting of results

Consolidated Health Economic Evaluation Reporting Standards (CHEERS) 2022 guidelines will be followed when reporting the health economic evaluation, in a format appropriate to stakeholders and policy makers. Any deviation from the HEAP will be described and justified in the final published report.

# 8 Appendix A: Amendment history

Lists details of all HEAP amendments whenever a new version of the HEAP is produced.

HEAP	Protocol	Name of	Date	Significant change(s) from previous
version	version	person who	changed	version together with reasons
no., Issue	no., Issue	made the		
date	date	change(s)		

#### 1 Introduction

This document details the proposed data presentation and analysis for the main paper(s) and final study reports from the NIHR-funded multicentre randomised controlled trial assessing the clinical effectiveness of supervised versus self-directed rehabilitation in improving ankle function for people aged 50 years and over after ankle fracture (AFTER). The results reported in these papers should follow the strategy set out here. Subsequent analyses of a more exploratory nature will not be bound by this strategy, though they are expected to follow the broad principles laid down here. The principles are not intended to curtail exploratory analysis (for example, to decide cut-points for categorisation of continuous variables), nor to prohibit accepted practices (for example, data transformation prior to analysis), but they are intended to establish the rules that will be followed, as closely as possible, when analysing and reporting the trial. This document follows published guidelines regarding the content of statistical analysis plans for clinical trial(1).

The analysis strategy will be available on request when the principal papers are submitted for publication in a journal. Suggestions for subsequent analyses by journal editors or referees, will be considered carefully, and carried out as far as possible in line with the principles of this analysis strategy. If reported, the analyses will be marked as post-hoc; the source of the suggestion will be acknowledged and the reader will be advised to rely on the pre-specified analysis for the interpretation of the results.

Any deviations from the statistical analysis plan will be described and justified in the final report of the trial. The analysis should be carried out by an identified, appropriately qualified, and experienced statistician, who should ensure the integrity of the data during their processing. Examples of such procedures include quality control and evaluation procedures.

Integral to this Statistical Analysis Plan (SAP) is the *SAP – Data Definitions and Tables* document which will include full detailed descriptions of all key outcomes, including their definition, generation and how they will be reported at the end of the study. These two documents should be read in tandem.

# 1.2 Changes from previous version of SAP

A summary of key changes from earlier versions of SAP, with particular relevance to protocol changes that have an impact on the design, definition, sample size, data quality/collection and analysis of the outcomes will be provided. Include protocol version number and date.

Version number Issue date	Author of this issue	Protocol Version & Issue date	Significant changes from previous version together with reasons
V1.0_14May2024		Protocol_V2.0_22May2023	Not applicable as this is the 1 st issue
			Add to or delete as required

## 2 Background and objectives

Ankle fractures are very common and the incidence of these fractures in the UK is highest among people aged 50 years and over (2, 3). As the population ages, a three-fold increase in these fractures is projected over the next two decades (4). The mechanism of injury for people aged over 50 is usually a fall from standing height; the fracture is then defined as a fragility fracture (5).

Treatments for ankle fractures range from non-surgical management through application of plaster casts or boots to surgical fixation. A recent trial including adults aged 60 years and over found that, regardless of the initial fracture management, post-injury reduced ankle function and walking abnormalities remain at 6 months post-injury (6, 7). Ankle movement restrictions during weight bearing are usually lifted by the orthopaedic team six weeks after injury. At this stage, national guidance is that patients should be advised to gradually resume activities. Data has shown that, in addition to the advice, some patients are referred to see a physiotherapist for supervised rehabilitation. Physiotherapy after ankle fracture aims to support patients during the recovery period and provide individualised progressive exercise to improve muscle strength, range of motion, gait and balance. However, the referral patterns vary from hospital to hospital (7) and there is no national guidance on whether further rehabilitation under the supervision of a physiotherapist should be provided.

Previous research in younger adults found additional physiotherapy did not improve recovery, but it is not clear whether older adults would benefit. Moreover, extra physiotherapy could bring cost burden to the health service.

Therefore, the aim of this pragmatic, parallel-group, randomised controlled superiority trial is to evaluate the clinical and cost-effectiveness of supervised versus self-directed rehabilitation in improving ankle function for people aged 50 years and over with ankle fractures.

# 2.1 Objectives

**Table 1** Primary and secondary objectives and endpoints.

	Objectives	Outcome Measures	Timepoint(s)
Primary	Ankle Function	Olerud and Molander Ankle Scale (OMAS)	6 months post- randomization
Secondary	Ankle Function	OMAS	Baseline, 2 and 4 months post-randomization
	Health-related quality of life	EQ-5D-5L	Baseline, 2, 4 and 6 months post- randomization
	Pain	Pain sub-scales of the EQ-5D-5L and OMAS	Baseline, 2, 4 and 6 months post- randomization
	Physical Function	PROMIS Physical Function	Baseline, 4 and 6 months post-randomization
	Self-efficacy	Self-Efficacy Exercise Score (SEE)	Baseline, 4 and 6 months post-randomization
	Exercise adherence	Self-reported exercise frequency	2, 4 and 6 months post- randomization
	Complications	Complications Questionnaire and Case Report Form	2, 4 and 6 months post- randomization
	Resource use	Health economics questionnaire	2 and 6 months post- randomization

## 3 Study METHODS

## 3.1 Trial Design/framework

AFTER is a multi-centre, parallel-group, superiority individually randomised controlled trial assessing the clinical effectiveness of supervised versus self-directed rehabilitation in improving ankle function for people aged 50 years and over after an ankle fracture. The trial will be conducted at secondary care trauma departments in a minimum of 20 NHS hospitals and their related physiotherapy services.

#### 3.2 Randomization and Blinding

The randomization will be on a 1:1 basis to supervised versus self-directed rehabilitation, using a validated computer randomization program managed through a secure (encrypted) web-based service by the Oxford Clinical Trials Research Unit (OCTRU). Randomization will use a minimisation algorithm to ensure balanced allocation across the two treatment groups, stratified by centre and initial fracture management (surgical vs non-surgical). The first few participants will be randomised by simple randomization to seed the minimisation algorithm and a probabilistic element introduced to the algorithm to ensure the unpredictability of intervention allocation.

Full details of the randomization are available in AFTER\_RandomizationAndBlindingPlan\_V1.0\_27Jul2022, stored in the confidential statistical section of the Trial Master File (TMF).

Due to the nature of the intervention, it is not possible to blind participants or those delivering the intervention. The local research team at recruiting centres will also not be blinded to the treatment allocation.

## 3.3 Sample Size

292 (146 per arm) participants providing primary outcome data at 6 months are required to detect a difference of 8 points on the OMAS score with an estimated standard deviation of 21 with 90% power and 5% (2-sided) significance. The minimum clinically important difference for the OMAS selected in surgical trials has usually been 10 points but for this trial of physiotherapy we have chosen a smaller difference of 8 points, which is likely to be clinically important and was supported by our patient advisory group. The chosen standard deviation of 21 is based on the AIM trial (6) (SD 21.7) and the feasibility study data (SD 20.5 based on 32 participants having reached the 6 month time-point). This equates to a standardised effect size of 0.38, a small to moderate effect. In the AFTER feasibility study there was 11% loss to follow-up (those not providing the primary outcome data). In order to allow for potential loss to follow-up of participants in the definitive trial we have inflated the sample size by 15% to aim for a minimum of 344 participants (172 per arm).

# 3.4 Statistical Interim Analysis, Data Review and Stopping guidelines

The study conduct and data safety will be discussed in the Trial Oversight Committee (TOC). The Trial Oversight Committee (TOC), which includes independent members, provides overall supervision of the trial on behalf of the funder. Its terms of reference is drawn up in a TOC charter (stored in AFTER\_TOCCharter\_V1.0\_18Aug2022) which outlines its roles and responsibilities. Full details of the data planned to be reported at the TOC meeting are available in the TOC report template (AFTER\_TOCTemplate\_V1.0\_17Aug2022).

There is no interim analysis planned for this trial. The trial is considered low risk so does not have a separate Data Safety Monitoring Committee (DSMC).

3.5

# 3.6 Timing of Final Analysis

The final analysis will be conducted after the last participant has reached the 6 month time period, and the data has been received, cleaned, and finalised.

#### 3.7 Blinded analysis

A blinded analysis (i.e. a review of the data prior to details of the interventions being added to the dataset) will be performed to look into the distribution of variables, missing data distributions, outliers and to finalise the per protocol population. The blinded analysis will be undertaken prior to the final datalock.

#### 3.8 Statistical Analysis Outline

The primary analysis population will be the intention-to-treat population (ITT), that is participants will be analysed in the group in which they were randomised regardless of what treatment they received. The analyses will be repeated for the per protocol (PP) population. The per protocol population will exclude participants who did not receive the allocated treatment and participants with major protocol deviations, this will be finalised using blinded data prior to

the final datalock. Standard descriptive statistics will be used to describe the demographics between the treatment groups reporting means and standard deviations or medians and interquartile ranges as appropriate for continuous variables and numbers and percentages for binary and categorical variables. Standard statistical summaries and graphical plots will be presented for the primary outcome measure and all secondary outcome measures.

The OMAS score at 6 months is the primary outcome in this study and will be compared between treatment groups as the dependent variable in a mixed-effects linear regression model including outcome information at intermediate time-points. This model will adjust for stratification factors (initial fracture management; operative or non-operative) and baseline OMAS score. A random effect will be included to account for heterogeneity due to recruitment centres. The treatment effect will be based on adjusted mean differences at 6 months and will be reported together with their 95% confidence intervals.

We will also undertake a Complier Average Causal Effect (CACE) analysis which essentially compares the "compliers" in each group. The CACE analysis will be undertaken using the definition of full compliance in the intervention group – defined as receiving a minimum of 4 physiotherapy sessions. Partial compliance is receiving at least one physiotherapy session (i.e. starting the treatment), which will be used in the per-protocol analysis. This will provide supporting evidence to any findings from the principal analysis. Subgroup analysis by surgical vs non-surgical treatment of the fracture will be undertaken, using a treatment by subgroup interaction term and will be presented using forest plots.

Similar methods to the primary outcome will be used to analyse continuous secondary clinical outcomes and patient reported outcomes. Complications will be reported by type for each intervention group, and, if appropriate, compared between the two groups using logistic regression models.

## 4 Statistical Principles

## 4.1 Statistical Significance and Multiple Testing

There is no multiple testing as only a single primary outcome is considered. Therefore, the significance levels used will be at the 2-sided 5% level and 95% confidence intervals will be reported. P-values will not be reported for subgroup exploratory analyses, the analyses results will be presented as forest plots with 95% confidence intervals. Any analyses that are not pre-specified will use the stricter 1% significance level and will be stated clearly as not included in the SAP.

## 4.2 Definition of Analysis Populations

The primary analysis population will be the intention-to-treat population (ITT), that is participants will be analysed in the randomised group in which they were allocated to regardless of what treatment they received. Patients with baseline outcome and at least one post-randomization outcome will be included in the analysis.

[figure not shown]
The analyses will be repeated for the per protocol (PP) population. The per protocol population will exclude participants who did not receive the allocated treatment and participants with major protocol deviations.

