## 1 Background and rationale

## 1.1 Purpose of the health economic analysis plan

The purpose of this health economic analysis plan (HEAP) is to describe the analysis and reporting procedure intended for the economic analyses to be undertaken. The analysis plan is designed to ensure that there is no conflict with the protocol and associated statistical analysis plan (SAP) and it should be read in conjunction with them. This HEAP largely follows the guidance as suggested by Thorn et al. This document has been written based on information contained in the trial protocol version 2.0, dated 22 May 2023 and SAP version 1.0, dated 14 May 2024.

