## 5 Data analysis

The data analysis will be conducted once all participants have been followed for six months after randomization; no interim analysis will be undertaken. The data analysis will include a within-trial analysis using imputed data that will include all randomised participants, which is in accordance with the "intention to treat" (ITT) principle, taking a sixmonths' time horizon.

There will be no discounting of costs and benefits as the follow-up period is less than one year. Utilisation of resource use items will be summarised by trial allocation group and follow-up period and differences between groups will be analysed using t-tests for continuous variables and Pearson chi-squared ( $\chi^2$ ) test for categorical variables. Means and standard errors for values of each cost category will be estimated by treatment allocation and follow-up period. Mean differences in costs and QALYs between the treatment groups will be estimated using t-tests and the bootstrap 95% confidence interval that will be computed based on 10,000 replications. This bootstrap will use Monte Carlo simulations to resample many datasets based on the original data.

Cost and QALY data will be combined to calculate incremental cost-effectiveness ratios (ICERs) and net monetary benefit (NMB) statistics from the NHS and PSS perspective in the primary economic analysis. The primary economic analysis will use incremental cost-effectiveness thresholds of £20,000 and £30,000 per QALY as recommended by NICE. An additional £15,000 per QALY cost-effectiveness threshold will also be included to reflect recent trends in healthcare decision-making.

All analyses will be carried out using appropriate analytical software such as R or STATA. The relevant package and version number will be recorded in the health economics report.

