## 6.2 Analysis Methods

## 6.2.1 Primary outcome analysis

The OMAS at 6 months is the primary outcome. Raw summary statistics (mean and standard deviation) will be calculated and reported by treatment arm for each time point.

The treatment difference between the two groups (self-directed rehabilitation and supervised rehabilitation) will be analysed using a mixed effect linear regression model. The OMAS at all follow-up time points will be the dependent variable (panel data) and the independent variable will be the interaction between treatment group and follow-up time points. This model will adjust for stratification factors of randomization (recruitment centre and initial fracture management (operative vs non-operative)), age in years, and sex at birth as fixed effects in the model.

Sensitivity analyses will be conducted to check the robustness of the analysis results. The analyses will include a partially-adjusted model, per protocol analysis and CACE analysis. A partially-adjusted model will only include baseline OMAS as its sole adjustment variable. Per-protocol analysis will only include participants at least partially compliant in the supervised rehabilitation arm to their allocated treatment (1 or more physiotherapy sessions in supervised rehabilitation arm), and will be conducted for the adjusted model. The per-protocol analysis will also exclude participants who did not receive the self-directed rehabilitation materials when allocated to self-directed rehabilitation.

Complier Average Causal Effect (CACE) analysis:

CACE analysis seeks to compare outcomes for individuals in the intervention condition who complied with treatment with individuals in the control group who would have complied with treatment given the opportunity to do so. The two treatment groups for the AFTER trial are supervised rehabilitation (intervention) and self-directed rehabilitation (control).

Participants in the intervention arm will be defined as non-compliers to the control arm if they have not met the adherence definition: Full compliance is defined as receiving a minimum of 4 physiotherapy sessions. However, it is unlikely for participants in the control arm to crossover to the intervention arm, therefore the per-protocol analysis

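### The SAP's primary ITT set requires a baseline value, so a participant with a recorded follow-up OMAS but no baseline OMAS is dropped; the likely cost is a little precision.

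*SAP*

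**What the plan says.** SAP section 3.8 defines the primary population by allocation alone: "participants will be analysed in the group in which they were randomised regardless of what treatment they received". Section 4.2 opens in the same way ("The primary analysis population will be the intention-to-treat population (ITT), that is participants will be analysed in the randomised group") and then narrows the set: "Patients with baseline outcome and at least one post-randomization outcome will be included in the analysis".

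Other parts of the document bear on this rule:

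- **Section 3.3** counts the participants needed as those who provide the primary outcome at 6 months, and defines loss to follow-up as not providing it. Baseline plays no part in that count.
- **Section 6.3** says that all data on the collection forms will be used. It relies on a missing-at-random mixed model with a delta-shift sensitivity analysis, and gives no rule for a missing baseline.
- **Section 3.8** puts baseline OMAS in the primary model: "This model will adjust for stratification factors (initial fracture management; operative or non-operative) and baseline OMAS score". The detailed model in section 6.2.1 lists centre, fracture management, "age in years, and sex at birth as fixed effects in the model", and does not list baseline OMAS.
- **Table 1** shows no baseline measurement for exercise adherence, complications or resource use.
- **Section 5 of the health economic analysis plan (HEAP)** describes its ITT analysis as "a within-trial analysis using imputed data that will include all randomised participants".

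**The concern.** The condition in section 4.2 has two halves, and they do different things.

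Requiring at least one follow-up value removes nobody who could inform the primary model, because a participant with no follow-up OMAS contributes no outcome to a likelihood-based mixed model.

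Requiring a baseline value does remove information. A participant whose 6-month OMAS is on file is excluded only because an earlier questionnaire is missing. The same happens for every other outcome that has a baseline measurement, such as EQ-5D-5L, pain, PROMIS Physical Function and self-efficacy.

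Three things are at stake: recorded outcomes are left unused, the ITT label does not describe the set being analysed, and the condition cannot be applied as worded to outcomes with no baseline. There is also a consequence for the sensitivity analysis. If the section 4.2 set governs the delta analysis as well, participants with no follow-up at all fall outside it, although the missing-at-random assumption matters most for them.

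**Working it through.** **1. The passages side by side**

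| Place | Who is in the analysis |
|---|---|
| SAP 3.8 | Participants as randomised; no data condition |
| SAP 4.2 | As randomised, with a baseline value and at least one follow-up value |
| SAP 3.3 | Sample size counts everyone with a 6-month OMAS |
| SAP 6.3 | All data collected will be used |
| HEAP 5 | All randomised, through imputation |

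A participant with a follow-up OMAS and no baseline OMAS is in under 3.8, counted under 3.3 if the 6-month score is present, used under 6.3, and out under 4.2. Nothing else in the document brings that participant back.

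**2. The plan's own sample size**

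Inputs from section 3.3: difference 8 points, SD 21, two-sided 5%, power 90%, loss 15%.

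For a two-sample t-test with *m* per arm, the noncentrality is (8/21) × √(*m*/2) on 2*m* − 2 degrees of freedom.

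- *m* = 146: noncentrality 0.38095 × √73 = 3.255, power 0.9004. This reproduces 292.
- 292 / (1 − 0.15) = 343.5, rounded up to 344. This reproduces the recruitment target.

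No figure in the plan is wrong.

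**3. Effect of the baseline condition**

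The document gives no rate of missing baseline. I assume 2% and 4% of those with the primary outcome, and count whole participants.

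*Full 15% loss:* 344 × 0.85 = 292.4, so 292 have the outcome.

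| Missing baseline (assumed) | Dropped | Left (per arm) | Power |
|---|---|---|---|
| 0% | 0 | 292 (146) | 90.0% |
| 2% | 292 × 0.02 ≈ 6 | 286 (143) | 89.4% |
| 4% | 292 × 0.04 ≈ 12 | 280 (140) | 88.8% |

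*11% loss, as in the feasibility study (section 3.3):* 344 × 0.89 = 306.2, so 306 have the outcome.

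| Missing baseline (assumed) | Dropped | Left (per arm) | Power |
|---|---|---|---|
| 0% | 0 | 306 (153) | 91.3% |
| 2% | 306 × 0.02 ≈ 6 | 300 (150) | 90.8% |
| 4% | 306 × 0.04 ≈ 12 | 294 (147) | 90.2% |

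At 11% loss the margin is 306 − 292 = 14 participants. Missing baseline would have to exceed 14/306 = 4.6% before the count fell below 292. These are unadjusted t-test figures and take no credit for precision gained from baseline or repeated measures.

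**4. Bias**

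Section 4.2 contrasts baseline with post-randomization outcomes, and Table 1 and HEAP section 4.3 list baseline apart from the post-randomization time points. The natural reading is that baseline comes before allocation. If so, whether it was completed cannot depend on arm, and excluding on it leaves the between-arm contrast unbiased even if non-completers have a different prognosis.

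**The case against.** The strongest reply is that the rule rarely bites. Baseline questionnaires are often completed at enrolment, the expected losses are a handful, and at 11% loss to follow-up the required 292 is still met. The companion document on data definitions and tables, which section 1 calls integral to the SAP and which is not shown here, may also deal with a missing baseline. All of this stands as a limit on the size of the point. It does not resolve the conflict in wording between sections 3.8, 4.2 and 6.3.

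A reader might infer three stronger things that the document does not support.

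- **That the randomised comparison is broken.** Selection on a measurement taken before allocation costs precision and perhaps representativeness. It would bias the contrast only if baseline could be completed after allocation was known. The trial is open-label and the document does not state the timing outright, so this cannot be excluded, but nothing in the text points to it.
- **That the SAP and HEAP hold two conflicting ITT principles.** Both analyse participants as randomised. The HEAP reaches all randomised participants by imputation, while the SAP uses a likelihood model under missing at random. Most of the difference between the sets is participants with no follow-up, which is a matter of method and would remain after the repair below.
- **That every secondary outcome loses participants.** Exercise adherence, complications and resource use have no baseline, so for them the condition is inapplicable.

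**Conclusion.** The point holds as a minor one. Section 4.2, followed literally, discards recorded outcomes from participants without a baseline value. That is inconsistent with the as-randomised definition in section 3.8 and with the promise in section 6.3 to use all data collected.

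The likely effect is a small loss of precision. With the 15% loss allowance fully used, power falls by about 0.6 to 1.2 percentage points, from 90.0% to 89.4% or 88.8%. At 11% loss it remains above 90%. Both results rest on an assumed 2 to 4% missing baseline, a rate the document does not give. The conclusion that bias between arms is unlikely rests on baseline having been recorded before randomisation, which is implied and not stated.

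**What to change.** 1. **Section 4.2:** replace the inclusion sentence so that all participants with at least one follow-up OMAS are analysed as randomised, whether or not a baseline value was recorded. Apply the corresponding rule to the other outcomes, and do not apply a baseline condition to outcomes that have none.
2. **Missing baseline:** state that, where a model adjusts for baseline, a missing value is replaced by the overall baseline mean. A missing-indicator method or a constrained longitudinal model would also serve. Settle at the same time whether the primary model includes baseline OMAS, since sections 3.8 and 6.2.1 differ on this and it decides whether any such rule is needed there.
3. **Section 6.3:** run the delta sensitivity analysis on all randomised participants, including those with no follow-up.
4. **SAP and HEAP:** add a sentence saying that the SAP primary set (participants with any follow-up) and the HEAP imputed set (all randomised) differ because of the missing-data method. Do not describe them as identical.

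If the present restriction is kept, call the set modified ITT. The cost is a few sentences and a small change to the analysis code; no further data collection is needed.
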